5.4 Study Sample

Each subject must meet all of the following inclusion criteria and none of the exclusion criteria at baseline (Visit 2, day 0) in order to participate in this study.

⁶ To be completed on all women <60 years of age.

⁸ Subjects will be instructed to fast for 10-14 h and to avoid of alcohol 3 d prior to test visits. Subjects will be queried about compliance with these instructions.

⁹Capillary glucose concentrations will be measured at each clinic visit using an FDA-approved glucometer to ensure adequate fasting (10-14 h). Visits may be rescheduled for non-compliance, in the judgment of the Clinical Investigator.

¹⁴Inquiring about AEs will occur with an open-ended question at the beginning and end of study visits.

5.4.1 Inclusion Criteria

- 1. Subject is a generally healthy male or female, 18-65 years of age, inclusive.
- 2. Subject has a score of 7 to 10 on the Vein Access Scale at Visit 1 (day -7).
- 3. Subjects exhibits a body weight >60 kg and has a BMI of \geq 18.0 and \leq 32.0 kg/m² at Visit 1 (day -7).
- 4. Subject is willing to avoid use of any over-the-counter medications and/or dietary supplements (vitamins, minerals and/or other supplements) within 3 d prior to visit 1 (day -7) and/or prescription medications (except for stable-dose oral contraceptives) within 14 d prior to visit 1 (day -7) and throughout the study period.
- 5. Subject is willing to avoid alcohol 3 d prior to each test visit (Visits 2, 3, and 4; days 0, 7, and 14).
- 6. Subject is willing to avoid grapefruit and/or grapefruit juice 3 d prior to each test visit (Visits 2, 3, and 4; days 0, 7, and 14).
- 7. Subject is willing to maintain habitual diet, physical activity patterns, and body weight throughout the trial.
- 8. Subject is a non-user of all tobacco, smoking products (including, but not limited to cigarettes, cigars, chewing tobacco, e-cigarettes), and nicotine products (e.g., nicotine gum and/or nicotine patches) within 6 months of Visit 1 (day -7) and has no plans to change status during the study period.
- 9. Subject has no health conditions that would prevent him/her from fulfilling the study requirements as judged by the Clinical Investigator on the basis of medical history and routine laboratory test results.
- 10. Subject understands the study procedures and signs forms providing informed consent to participate in the study and authorizes the release of relevant protected health information to the Clinical Investigator.

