5.2 Study Design

This is an unblinded, crossover, sequential three dose study (Figure 1). The study will include one screening visit (Visit 1; day -7) and three test visits (Visits 2, 3, and 4; days 0, 7, and 14) with at least a 6-d washout between test visits.

[figure not shown]

Figure 1.

At Visit 1 (day -7), subjects will provide informed consent and undergo screening assessments including evaluations of medical history, prior/current medication/ supplement use, inclusion and exclusion criteria, height, body weight, BMI, vital signs, and Vein Access Scale (Appendix 2). A fasting capillary blood glucose will be assessed to establish each subject's fasting level and an in-clinic urine pregnancy test (all women <60 years of age) will also be obtained. Additionally, a fasting (10-14 h) blood sample will be collected for a chemistry profile and hematology panel. Study instructions will also be provided [fasting compliance (10-14 h, water only) and avoidance of alcohol 3 d

prior to test visits (Visits 2, 3, and 4; days 0, 7, and 14]. Subjects will then be dispensed a 24-h Diet Record (Appendix 3) with instructions to record intake the day prior to Visit 2 (day 0).

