5.3 Flowchart

			Test Days	
	Screening	Low Dose	Medium Dose	High Dose
Visit ¹	1	2	3	4
Days	-7	0	7	14
Informed Consent/HIPAA ²	X			
Clinic Visit ³	X	X	X	X
Medical History	X			
Chemistry Profile ⁴	X			
Hematology Panel ⁵	X			
In-clinic Urine Pregnancy Test ⁶	X			
Vein Access Scale Assessment ⁷	X			
Study Instructions/Query ⁸	X	X	X	X
Enrollment		X		
Capillary Glucose ⁹	X	X	X	X
Dispense 24-h Diet Record ¹⁰	X	X	X	
Collect/Review/Copy 24-h Diet Record ¹¹		X	X	X
Pharmacokinetic Test ¹²		X	X	X
Backup Blood Samples ¹³		X	X	X
Adverse Event Assessment ¹⁴		X	Х	X

Footnotes:

¹ A period up to 21 d will be allowed between Visits 1 and 2 (days -7 to 0) and the washout period between Visits 2 and 3 (days 0 and 7) and Visits 3 and 4 (days 7 and 14) will be 6-13 d.

³Clinic visit procedures include measurement of height (Visit 1 only), body weight, BMI (first visit only), vital signs, and where appropriate, a review of inclusion/exclusion criteria (for eligibility at Visit 1 and for potential protocol deviations at subsequent visits), and concomitant medication/supplement use.

⁴The following will be performed as part of the fasting (10-14 h) chemistry profile: albumin, alkaline phosphatase, total bilirubin, direct bilirubin, calcium, chloride, creatinine, blood urea

² Health Insurance Portability and Accountability Act (HIPAA) for disclosure of protected health information. Signed document authorizes the use and disclosure of the subject's Protected Health Information by the Investigator and by those persons who need that information for the purposes of the study.

nitrogen (BUN), potassium, aspartate aminotransferase (AST), alanine aminotransferase (ALT), sodium, total protein, carbon dioxide (CO₂), osmolality, and glucose.

⁵The following will be performed as part of the fasting (10-14 h) hematology panel: white blood cell count (WBC), red blood cell count (RBC), hemoglobin concentration, hematocrit (as volume percent), mean cell volume (MCV), mean cell hemoglobin (MCH), mean cell hemoglobin concentration (MCHC), neutrophils, lymphocytes, monocytes, eosinophils, basophils and platelet count.

⁷Appendix 2.

¹⁰Subjects will complete a 24-h Diet Record identifying all food and beverages consumed the day prior to Visit 2 (day 0; Appendix 3). A clean copy of the 24-h Diet Record will also be provided with instructions for subjects to complete the record the day prior to Visits 3 and 4.

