7.1 Concomitant Medication/Supplements and Treatment

All concomitant medications/supplements used 30 d prior to Visit 1 (day -7) and during the study will be reported to the study personnel for assessment and recorded in the subject's eCRF.

Use of the medications/supplements described in the "Exclusion Criteria" section and Appendix 1 is not allowed during this study. If a subject requires any of these medications/supplements, the subject may not enter the study. If a subject uses any exclusionary medications/supplements once enrolled, a protocol deviation will be documented.

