Appendix 1: Examples of Exclusionary Medications, Supplements, and Foods This list is not intended to be comprehensive.

CLASS OF DRUG/PRODUCT	GENERIC/BRAND NAME
Excluded within 14 d prior o	f Visit 1 (day -7) and throughout the study
Prescription medication	All prescription medications except stable dose oral contraceptives (defined as same dose for the past 90 d prior to Visit 1; day -7)
Excluded within 3 d prior of	Visit 1 (day -7) and throughout the study
Over-the-counter medications	All over-the-counter medications
Dietary supplements	Any dietary supplement (including protein supplements)
Excluded within 3 d prior to	each test visit (Visits 2, 3, and 4; days 0, 7, and 14)
Grapefruit and/or grapefruit jui Alcohol	ice

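### No strontium-specific look-back at entry: a former daily strontium user can be enrolled with accumulated strontium, which would inflate Cmax, mainly at the low dose, if elimination is slow

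*Combined protocol and SAP*

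**What the plan says.** Inclusion criterion 4 (section 5.4.1) requires subjects to be willing to avoid over-the-counter products and "dietary supplements (vitamins, minerals and/or other supplements) within 3 d prior to visit 1 (day -7"), and prescription medicines other than stable oral contraceptives "within 14 d prior to visit 1 (day -7) and throughout the study period". Section 5.4.3 repeats these rules. Appendix 1 lists "Any dietary supplement (including protein supplements"), so a strontium supplement is barred from that point on, although strontium is not named. None of the 15 exclusion criteria in section 5.4.2 mentions prior strontium. Exclusion 13 concerns non-registered drug products.

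Section 5.2 places screening at day -7 and the three dosing visits at days 0, 7 and 14, "with at least a 6-d washout between test visits". Footnote 1 of the flowchart (section 5.3) states "A period up to 21 d will be allowed between Visits 1 and 2 (days -7 to 0") and gives no minimum. For the spacing of the study doses, the same footnote gives a range of 6 to 13 d.

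Section 7.1 says "All concomitant medications/supplements used 30 d prior to Visit 1 (day -7) and during the study will be reported", but past strontium use within those 30 d triggers no action. The screening laboratory panels do not include strontium. Every test visit has a pre-dose strontium sample. In section 6.1 the AUC outcomes are described as incremental from that sample; no baseline correction is stated for Cmax, λz or half-life.

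**The concern.** The entry rules treat the trial's own analyte like any other supplement. Someone who has taken strontium daily for months qualifies on the same terms as someone who took a multivitamin, by stopping 3 d before screening. The in-study washout deals with the residue of one dose, whereas a daily user brings in the residue of many.

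Doses always run low, medium, high, so a residual that fades over the study is confounded with dose. It raises the low-dose profile most and the high-dose profile least. The target is 10 enrolled and at least 6 completing, the analysis is descriptive, and one such subject is 1/10 to 1/6 of the data (10% to 17%).

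**Working it through.** **Inputs from the plan.** Supplement stop: 3 d before Visit 1. Prescription stop: 14 d before Visit 1. Visit 1 to first dose: 7 d nominal, 21 d maximum, no stated minimum. Washout: 6 d minimum. Doses: 170, 340 and 680 mg Sr, in that order, 7 d apart. The plan's 6 d reproduces as the days between dosing days 0 and 7: 7 − 0 − 1 = 6.

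**Step 1, calendar.** Supplement-free interval before the first dose = 3 + (Visit 1 to Visit 2 gap):
- nominal: 3 + 7 = 10 d
- longest: 3 + 21 = 24 d
- equal to the 6 d washout at a gap of 3 d; below it only at a gap of 1 or 2 d (4 or 5 d)
- prescription strontium: 14 + 7 = 21 d nominal

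**Step 2, accumulation.** Assumed, not in the documents: one compartment, linear kinetics, daily use to steady state, absorption phase ignored, half-life t of 24, 60 or 100 h. Residuals are multiples of the level from a single 170 mg dose.

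- Former user of D mg/d, d days after stopping: R = (D/170) × 2^(−24d/t) / (1 − 2^(−24/t))
- One 170 mg study dose, 6 d later: S = 2^(−144/t)

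| Half-life | 1/(1 − 2^(−24/t)) | R at 10 d, 170 mg/d | S at 6 d | R/S |
|---|---|---|---|---|
| 24 h | 2.00 | 0.002 | 0.016 | 0.12 |
| 60 h | 4.13 | 0.26 | 0.19 | 1.4 |
| 100 h | 6.53 | 1.2 | 0.37 | 3.4 |

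For 680 mg/d, R is four times larger: 0.008, 1.0 and 4.9.

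**Step 3, break-even at 10 d.** R = S when 2^(−96/t) = 1 − 2^(−24/t). With x = 2^(−24/t) this is x⁴ + x = 1, so x ≈ 0.7245 and t ≈ 52 h. For 680 mg/d against one 170 mg dose, 4x⁴ + x = 1 gives t ≈ 30 h. If the study-dose interval is counted as 7 elapsed days, x³ + x = 1 gives t ≈ 44 h for 170 mg/d.

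**Step 4, effect on each outcome in the affected subject (170 mg/d, 10 d).**

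*Cmax, uncorrected.* With absorption ignored, relative inflation is R(10 d)/1 at the low dose, R(17 d)/2 at the medium and R(24 d)/4 at the high:

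| Half-life | Low | Medium | High |
|---|---|---|---|
| 24 h | 0.2% | <0.1% | <0.1% |
| 60 h | 26% | 1.9% | 0.1% |
| 100 h | 124% | 19% | 3.0% |

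If the other subjects have similar Cmax, the low-dose mean rises by one-tenth to one-sixth of this: 2.6% to 4.3% at 60 h and 12% to 21% at 100 h.

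*iAUC to 12 h.* With k = ln2/t and a = (1 − e^(−12k))/k, subtracting the pre-dose value leaves a relative bias of R(a − 12)/a. For a = 10.14, 11.21 and 11.51 this is −0.04%, −1.8% and −5.2% in that subject.

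*λz and half-life.* The concentration is (A + R)e^(−kt), where A is the level from the study dose. The residual and the study dose decay at the same rate, so the raw terminal slope is unchanged. Bias arises only if a constant baseline is subtracted before the slope is fitted, or if the kinetics are multi-compartment.

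**The case against.** A reader might infer that nothing stops recent strontium users from enrolling. The documents do not support that: criterion 4, section 5.4.3 and Appendix 1 bar any supplement from 3 d before Visit 1 onward. What is missing is a look-back sized for the analyte.

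A reader might also infer that the run-in is shorter than the washout. On the planned schedule it is longer, 10 d against 6 d. The missing minimum in footnote 1 does leave room for less than 6 d, but only with a gap under 3 d. That departs from day −7 and clashes with the 3 d alcohol instruction given at Visit 1. It also leaves little time for screening results from an outside laboratory. The 4 d case should not carry the argument.

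Nor does a false dose trend in λz and half-life follow. Step 4 shows the raw slope is unchanged in this model, and the iAUC to 12 h moves little. These objections stand and narrow the point to Cmax.

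The plan also has partial safeguards. The 30 d history would show most such users, and the pre-dose sample would show carry-in. Section 6.3 allows data to be excluded if documented before database lock. But these act after enrolment or by judgement, and dropping a subject from a set of 6 to 10 is costly. Finally, the documents give neither a half-life nor how common strontium use is among eligible volunteers. That is correct, and it limits the severity.

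**Conclusion.** The gap holds in a limited form. The entry rules contain no strontium-specific look-back, so a former daily user can enter after a nominal 10 d. Whether this matters depends on a half-life that the plan does not give and that the study itself sets out to measure. At 24 h the effect is negligible. Above about 52 h the residual from 170 mg/d exceeds what the in-study washout leaves after one low dose. The exposed outcome is mainly Cmax: at assumed half-lives of 60 to 100 h, roughly 26% to 124% too high at the low dose in the affected subject, fading to 3% or less at the high dose. The iAUC to 12 h is largely protected, and λz and half-life are unaffected in this model unless a constant baseline is removed first.

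These sizes rest on one-compartment linear kinetics, steady daily use of 170 mg up to the stopping point, and at least one such volunteer enrolling. This is a cheap improvement, not a flaw that undermines the study.

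**What to change.** Add one line to section 5.4.2 and one row to Appendix 1: *Subject has used any strontium-containing supplement or medicine within 30 d prior to Visit 1.* The information is already collected under section 7.1, so the rule can be applied at Visit 1 without a new visit, assay or form. The 3 d rule for other supplements can stay.

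On the nominal schedule the interval becomes 30 + 7 = 37 d. By the Step 2 formula, the residual from 170 mg/d is then at most 0.014 of a low-dose level across the assumed half-lives (100 h: 6.53 × 2^(−8.88)). Even with a 1 d gap between Visits 1 and 2 (31 d) it is 0.038, so the rule also covers the missing minimum in footnote 1.

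The cost is that a few volunteers become ineligible.

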5.4.2 Exclusion Criteria

- 1. Subject has abnormal laboratory test results of clinical significance at Visit 1 (day -7) at the discretion of the Investigator. One re-test will be allowed on a separate day prior to Visit 2 (day 0), for subjects with abnormal laboratory test results.
- 2. Subject has a known allergy or sensitivity to any of the ingredients in the study products and/or any ingredients of the meals provided.
- 3. Subject has a history of anaphylaxis, a documented hypersensitivity reaction, and/or a clinically important reaction to any drug.
- 4. Subject has a history or presence of clinically important endocrine (including hyperparathyroidism, type 1 or 2 diabetes mellitus and/or hypoglycemia), cardiovascular (including, but not limited to history of myocardial infarction, peripheral arterial disease, stroke), pulmonary (including uncontrolled asthma), hepatic, renal, hematologic, immunologic, dermatologic, neurologic (such as Alzheimer's or Parkinson's patients), rheumatic (including gout), biliary, and/or psychiatric disorders (including depression and/or anxiety disorders), that, in the opinion of the Investigator, could interfere with the interpretation of the study results.

- 5. Subject has had a loss of 400 mL of blood (e.g., blood/plasma donation) during the prior 30 d of visit 2 (day 0).
- 6. Subject has a history or current GI disorder that, in the judgment of the Investigator, may have the potential to disrupt normal digestion and absorption.
- 7. Subject has a history or presence of cancer in the prior two years, except for non-melanoma skin cancer.
- 8. Subject has a history of bariatric surgery for weight reducing purposes.
- 9. Subject has recently (within 6 months prior to Visit 1; day -7) had a weight loss or gain >4.5 kg.
- 10. Subject has uncontrolled hypertension (systolic blood pressure ≥160 mm Hg or diastolic blood pressure ≥100 mm Hg) as defined by the blood pressure measured at Visit 1 (day -7). One re-test will be allowed on a separate day prior to Visit 2 (day 0), for subjects with abnormal blood pressure.
- 11. Subject has extreme dietary habits (e.g., Atkins diet, very high protein, vegetarian, intentional consumption of a high fiber diet), in the opinion of the Clinical Investigator.
- 12. Subject is a female, who is pregnant, planning to be pregnant during the study period, lactating, or is of childbearing potential and is unwilling to commit to the use of a medically approved form of contraception throughout the study period. The method of contraception must be recorded in the source documentation.
- 13. Subject has been exposed to any non-registered drug product within 30 d prior to visit 1 (day -7).
- 14. Subject has a recent history of (within 12 months of screening; Visit 1; day -7) or strong potential for alcohol or substance abuse. Alcohol abuse is defined as >14 drinks per week (1 drink = 12 oz beer, 5 oz wine, or 1½ oz distilled spirits).
- 15. Individual has a condition the Clinical Investigator believes would interfere with his or her ability to provide informed consent, comply with the study protocol, which might confound the interpretation of the study results, or put the subject at undue risk.

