Blood samples will be obtained via the indwelling venous catheter or venipuncture at t=3,4,5,6, and $8 \text{ h} \pm 5 \text{ min}$, where t=0 h is the start of study product consumption, for the PK analysis of serum strontium. Subjects will be administered a standard lunch (immediately following the t=6 h blood draw), a standard snack (immediately following the t=8 h blood draw) and a standard dinner (at t=10 h). Subjects will consume the meals/snack in their entirety within 30 min. Following the final blood draw at $t=12 \text{ h} \pm 5 \text{ min}$, AEs will be assessed. Subjects will be dispensed a blank/new 24-h Diet Record to record all food and beverage consumed the day prior to Visit 3 (day 7); as well as a copy of the completed 24-h Diet Record (from day -1) with instructions to replicate the same food and beverage intake as closely as possible the day prior to the subsequent visit. Study instructions will also be provided [(i.e., fasting compliance (10-14 h, water only) and avoidance of alcohol 3 d prior to the subsequent test visits].

At Visits 3 and 4 (days 7 and 14), subjects will return to the clinic for clinic visit procedures (i.e., vital signs; body weight; review inclusion and exclusion criteria for relevant changes, and concomitant medication/supplement use review). AEs will be

assessed and subjects will be queried about study instructions compliance. The 24-h Diet Record will be collected and study staff will review the 24-h Diet Record to compare food and beverage consumption to the day -1 recall for consistency. If the subject's food intake is not consistent from the 24-h Diet Record reviewed at Visit 2 (day 0), the study staff should contact the Project Manager before continuing the visit as the test visit may require rescheduling. Subjects will then crossover to the next sequential dose of study product [medium dose at Visit 3 (day 7) and high dose at Visit 4 (day 14)] and repeat the PK test described above for Visit 2.

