7.3.7 Pregnancy

There are no adequate and well-controlled studies on strontium L-lactate use in pregnant women, therefore, pregnant or lactating women will be excluded from the study. Additionally, the outcome variables measured would be expected to be affected by pregnancy and lactation. All female participants <60 years of age will undergo in-clinic urine pregnancy testing at Visit 1 (day -7). Pregnant or lactating women will be excluded from the study and women of childbearing potential will be required to use appropriate contraceptive methods to avoid pregnancy. Documentation of contraception method must be recorded in the source chart.

Although pregnancy is not a SAE, all pregnancies occurring in enrolled subjects will be reported within 24 h of notification. The Clinical Investigator will immediately notify the Sponsor, the Project Manager and the IRB about the pregnancy. Should a female subject become pregnant at any time after randomization the Clinical Investigator will be required to follow the subject through the pregnancy term and report to Biofortis Innovation Services the course of the pregnancy including perinatal and neonatal outcomes.

8. Conduct of the Study

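### Exclusion 12 ties contraception to the study period, so on the ordinary reading none is required after the day of the highest dose (680 mg Sr)

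*Combined protocol and SAP*

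**What the plan says.** Exclusion 12 in Section 5.4.2 bars a woman who plans a pregnancy within the study period, or who "is of childbearing potential and is unwilling to commit to the use of a medically approved form of contraception throughout the study period". The protocol does not define that period. Sections 5.4.1 and 5.4.3 use the same term for the tobacco and medication rules.

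Section 7.3.7 restates the requirement without an end date: "women of childbearing potential will be required to use appropriate contraceptive methods to avoid pregnancy". Its first reason for excluding pregnancy is that "There are no adequate and well-controlled studies on strontium L-lactate use in pregnant women". Its second is that pregnancy and lactation would be expected to affect the measured outcomes. The section also has pregnancies reported and followed to term: "Should a female subject become pregnant at any time after randomization" opens that rule.

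Section 5.2 sets one screening visit and three test visits, "with at least a 6-d washout between test visits". The doses rise in a fixed order, "medium dose at Visit 3 (day 7) and high dose at Visit 4 (day 14"), so the 680 mg Sr dose falls on the last visit. Footnote 1 of Section 5.3 gives the windows: "A period up to 21 d will be allowed between Visits 1 and 2", and a washout that, for Visits 2 to 3 and Visits 3 to 4 ("days 7 and 14) will be 6-13 d"), has both a lower and an upper limit.

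**The concern.** The commitment ends when the visits end, and the visits end on the day of the largest dose. A woman can comply fully with the protocol text and stop contraception that day. After 170 mg and 340 mg she remains committed for at least the washout, but only because she is still in the study. The plan does not present the washout as a contraception standard.

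The two reasons in Section 7.3.7 do not expire together. The concern about distorted outcomes ends with the last blood draw. The concern about missing pregnancy data lasts as long as absorbed strontium may be present, and the plan does not know how long that is. Section 2 says this product has not been tested in clinical trials, and Section 6.1 lists half-life among the outcomes. At stake is possible fetal exposure that the plan's own reasoning seeks to avoid. No trial estimate is affected.

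**Working it through.** This is mainly a check of the text against the schedule. The plan states no figure to reproduce.

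**1. When the commitment ends.** The last planned visit is Visit 4, nominal day 14. The 680 mg Sr dose is given at that visit, which closes after the 12 h sample (Section 5.6.6). Days of contraception required beyond the dosing day: 14 − 14 = 0.

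**2. Cover after each dose**, for a woman who continues to Visit 4:

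| Dose (Sr) | Visit | Commitment still running after the dose |
|---|---|---|
| 170 mg | 2 | at least 6 d |
| 340 mg | 3 | at least 6 d |
| 680 mg | 4 | none stated beyond the dosing day |

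If a 6-day washout means visits 7 d apart, as nominal days 0, 7 and 14 suggest, the first two entries become at least 7 d.

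**3. Whether another provision fills the gap.**

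- Section 7.3.7 requires contraception but gives no duration, so it supplies no interval after the dose.
- The pregnancy reporting and follow-up rule has no cut-off at Visit 4, but it acts only once a pregnancy is known.
- The 30-day follow-up page in Section 7.3.5 covers only subjects with an adverse event still open at the final visit, and is not linked to contraception.
- Pregnancy testing is at Visit 1 only (Section 5.6.2).
- The study instructions in Section 5.6.4 cover fasting and alcohol before test visits. They do not mention contraception.

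None of these sets an interval after the last dose.

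**4. Women affected.** Section 5.4.4 plans for half women and Section 6.2 for 10 enrolled: 0.5 × 10 = 5, approximately. The number of childbearing potential may be smaller, since ages run to 65.

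**5. Effect of a 6 to 7 d tail on the length of commitment.**

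| Spacing | Visit 1 to Visit 4 | With tail |
|---|---|---|
| Nominal | 7 + 14 = 21 d | 21 + 6 = 27 d, or 21 + 7 = 28 d |
| Widest, washout taken as the visit gap | 21 + 13 + 13 = 47 d | 47 + 6 = 53 d |
| Widest, visits one day further apart than the washout | 21 + 14 + 14 = 49 d | 49 + 7 = 56 d |

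**6. Illustration of persistence.** The documents give no half-life, so the values below are assumptions. With first-order elimination, the fraction of absorbed strontium remaining at time t is 0.5^(t / half-life).

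| Assumed half-life | Remaining at 12 h | Five half-lives |
|---|---|---|
| 12 h | 0.5^(12/12) = 50% | 60 h = 2.5 d |
| 24 h | 0.5^(12/24) = 71% | 120 h = 5 d |
| 60 h | 0.5^(12/60) = 87% | 300 h = 12.5 d |

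Under all three assumptions, at least half of the absorbed strontium is still present when Visit 4 closes. The last column shows that 6 to 7 d could be longer than needed or too short. The documents do not determine the right interval.

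**The case against.** The strongest objection is that the consent form is where a woman learns what she commits to, and it was not available for review. It may state a duration. This stands as a limit: the finding concerns the protocol text and does not show what subjects were told.

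Second, the study period is undefined, and some duties, such as pregnancy follow-up and the 30-day adverse event page, run past Visit 4. That is true, but neither sets a contraception interval. If the sponsor intends a longer period, the term needs a definition.

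Third, the washout separates crossover periods and is not a reproductive-safety interval, and the correct interval cannot be derived from the documents. This also stands. The washout comparison shows an inconsistency within the plan and supplies a minimum. It does not establish a risk period.

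Fourth, no reproductive hazard is shown. Section 2 says strontium salts have been given safely at up to 2 g daily for up to three years, and it contrasts this product with related salts that have been studied. That is fair context for three single doses, and no harm is claimed here. However, the statement covers normal subjects and subjects with osteoporosis. It does not address pregnancy, and Section 7.3.7 itself treats the lack of pregnancy data as a reason to exclude.

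The absence of an instruction review at Visit 4 is weak evidence, because the existing instructions prepare for a next test visit. It matters only because Visit 4 is the natural place for the new instruction.

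**Conclusion.** The concern holds. On the ordinary reading of the study period as Visit 1 to Visit 4, the protocol text requires no contraception after the day of the 680 mg Sr dose. Each smaller dose is followed by at least 6 d of cover (7 d counted as visit spacing).

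The size is small: at most about 5 of 10 subjects, three single doses, and no pharmacokinetic result changed. It is a point to consider, held with medium confidence. It rests on the ordinary reading of an undefined term and on the consent form not already stating a longer duration.

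**What to change.** In exclusion 12 and Section 7.3.7, extend both commitments (no planned pregnancy, and contraception) to a stated number of days after the last dose taken. Set that number no lower than the plan's minimum washout: 6 d, or 7 d if counted as visit spacing. The sponsor's medical staff should choose a longer interval if elimination data warrant it. In Sections 5.6.4 and 5.7.2, add a Visit 4 instruction that gives the end date and asks the subject to report any pregnancy in the interval. Align the consent form if it does not already say this.

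The cost is wording, with no added visit, procedure or analysis. At the 6 to 7 d minimum it adds about one week of commitment for at most about 5 women, and a woman planning a pregnancy in that week would be excluded. Without an added contact, a later pregnancy would still come to light only by self-report.
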